60 active subjects up to 100 participants will be enrolled. All enrollments will be voluntary. Participants will receive compensation for their participation. After obtaining informed consent and assent, participants will provide baseline demographic information, including: age, race/ethnicity, zip code of residence, health insurance provider, number of current and past partners, use of prior contraceptive methods, concomitant condom use, sexually transmitted infection history, age at menarche, menstrual cycle regularity, last menstrual period, weight and height. The date of etonogestrel implant insertion will be confirmed.

All patients using etonogestrel contraceptive implants will receive daily SMS texts in the evening via the Qualtrics SMS program asking them to respond with their bleeding pattern that day. If the SMS text messages are unable to connect to your personal cell phone we request an alternative cell phone number be given in order to reach you. We will record responses according to the World Health Organization definitions of bleeding: (a) bleeding day, (b) spotting day, (c) bleeding-free day [see Table I for WHO bleeding definitions]. At their initial follow-up visit 3 months after Nexplanon insertion, we will identify those who report “bothersome” bleeding patterns. For the purpose of this study, “bothersome” bleeding will be defined as prolonged and/or frequent bleeding, as characterized by World Health Organization-recommended definitions of bleeding. The definitions are listed in Table I.

Bleeding day	Any day with vaginal discharge containing blood that required more than 1 sanitary pad or tampon per day
Spotting day	Any day with vaginal discharge containing blood that required at most one sanitary pad or tampon per day
Bleeding-free day	A day during which neither bleeding nor spotting was reported
Bleeding-spotting episode	One or more consecutive days during which bleeding or spotting was entered in the diary, bounded by bleeding-free days
Amenorrhea	No bleeding or spotting days throughout the 90-day reference period
Infrequent bleeding	Less than three bleeding-spotting episodes in a 90-day reference period, excluding amenorrhea
Normal frequency	Three to five bleeding-spotting episodes in a 90-day reference period
Frequent bleeding	More than five bleeding-spotting episodes in a 90-day reference period

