Prolonged bleeding	Any bleeding-spotting episode (uninterrupted) lasting more than 14 days in the 90-day reference period

Table I: WHO bleeding descriptions and patterns

Norethindrone acetate (aygestin) will be used to manage bothersome bleeding. Patients will be prescribed aygestin 5 mg by mouth twice daily for one month, followed by aygestin 5 mg by mouth once daily for two months. Medication will then be discontinued. Patients will be evaluated in the office three months after medication initiation, and then again six months after medication initiation. If the patient is unable to take norethindrone acetate (aygestin) due to medical contraindications or cost, they will receive medroxyprogesterone acetate (provera) 10 mg once daily as alternate oral progesterone. Figure 1 below highlights the study design.

[figure not shown]

Figure 1: Study design

During the aygestin administration, patients will again receive daily SMS texts in the evening via the Qualtrics SMS program asking them to respond with their bleeding pattern that day. We will record responses according to the World Health Organization definitions of bleeding: (a) bleeding day, (b) spotting day, (c) bleeding-free day. Patients not reporting bothersome bleeding after the initial 90 days will continue to record bleeding via SMS texts for the next 6 months to serve as the control group (normal bleeding group).

Participants will be compensated as an incentive to increase daily participation. The participant will receive a pre-paid card if they respond to >70% of text messages over each 90-day cycle and attend the scheduled office visit. Patients will receive a \$5 pre-paid card at visit one (3 months after insertion of etonorgestrel implant), \$10 pre-paid card at visit two (6 months after insertion of etonorgestrel implant), and a \$15 pre-paid card at visit three (9 months after insertion of etonogestrel implant).

At the completion of the study, 9 months after enrollment, participants will receive a SMS text message via Qualtrics with a link to a 12 question follow up survey. The post study questionnaire will assess overall satisfaction with the etonogestrel implant and evaluate participants' perceptions of text messaging as a tool to collect information. See Appendix II.

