Participants who have already completed the 9 month study will receive an updated copy of the consent and assent form via mail with a request to sign the updated consent and assent forms. See Appendix III for a copy of a letter to be included with the updated consent and assent. Once the updated consent and assent are received by the investigators at Norton Children's Gynecology the post survey follow up will be sent to the participant by SMS text message via Qualtrics. Study participants who are seen in the office for their 9 month follow up visit will be re-consented in the office.

Patients diagnosed with a sexually transmitted infection during the course of the study will be removed from the study and their data will be excluded from analysis.

All completed demographic data collection forms and electronic menstrual calendars will be kept in a database, de-identified, and stored on a password-protected computer. Study size will be a convenience sample. Based on the current rate of etonogestrel implant insertions in our practice, it is anticipated that 30 participants can be recruited over a six-month period of time.

Data Collection and Analysis

All patients who meet the inclusion criteria and enroll in the study will be sent a text message daily for 90 days (3 months). The daily message will prompt the participant to indicate the bleeding level for the day. This single question will have 4 options:

1. Bleeding Day
2. Spotting Day
3. Bleeding Free Day
4. Prefer not to answer today.

On day 90, descriptive tallies of the responses will be done. Using SPSS v20, an algorithm will count the number of bleeding days, spotting days, and bleeding free days and prefer not to answer (PNA) days; the data record for each participant will contain four count variables (bleeding, spotting, free, PNA). Secondly, the algorithm will identify and tally –according to WHO guidelines in Table 1 - bleeding-spotting episodes (BSE), amenorrhea (AM), infrequent bleeding (IF), normal frequency of bleeding (NF), frequent bleeding (FB), and prolonged bleeding (PB).

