Participants who have at least a single episode of FB or PB will be assigned the label of “bothersome bleeding”. Those without a single episode of FB or PB will be labeled “normal bleeding”. Participants in the Bothersome Bleeding group will be offered aygestin to control the bothersome bleeding. Participants in the Normal Bleeding group will continue as before, with no additional medications. Following the principle of intent-to-treat, data from those in the Bothersome Bleeding group will be assigned to the aygestin group, despite that they are not taking it.

During the first month, participants in the Bothersome Bleeding group will take one 5 mg tablets of aygestin twice daily (morning and evening). After 30 days, the dose of aygestin will be halved, such that only one 5 mg tablet is taken daily. Sixty days

later, the Bothersome Bleeding group will discontinue aygestin. Ninety days later, both the normal group and the Bothersome Bleeding group will be re-evaluated.

Data Analysis

A descriptive table will be used to sort participants into Normal Bleeding and Bothersome Bleeding. Non-parametric and parametric statistics will be used to compare the demographics of these two groups.

A **dose-response curve** covering six months will be plotted for the Bothersome Bleeding group to visually reveal the impact of one month of 10 mg of aygestin vs. two months of 5 mg aygestin vs. three months 0 mg of aygestin. Plotted on the curve will be the group averages of the daily bleeding value (1 for no bleeding, .5 for spotting, 0 for bleeding). A second **no-dose curve** will be added to the X-Y plot for the six months of data from the Normal Bleeding group.

Repeated Measure Multivariate Analysis of Variance (RM-ANOVA) with a Between-Subjects variable included, will be conducted (assuming sufficient data is available – e.g., low PNA rates) to compare the first 30 day average bleeding value, the 90 day bleeding average, and the 180 day bleeding average between the two groups.

Planned post-hoc comparisons will evaluate changes between the control group and intervention group at the three time points.

Additional analyses may also include regression analysis to assess for predictive factors related to response to aygestin.

TIMELINE:

October 2014	IRB Submission
November 2014	Anticipated IRB Approval
November 2014 – July 2015	Data Collection
August – September 2015	Data Analysis

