Use of Norethindrone Acetate for Management of Bleeding Associated With the Etonogestrel Contraceptive Implant

NCT02353247

Nov. 14, 2016

Data Analysis Plan

The primary hypothesis was analyzed using repeated measures ANOVA (RM-ANOVA) with two groups and three measurements (summary statistics at day-90, day-180, and day-270). To have at least 80% *a-priori* power to detect a medium effect size ($f = 0.25$) at $\alpha = 0.05$, a total sample size of 28 was required with approximately equal sized groups. (G*Power version 3.1.9.2¹; Faul, Erdfelder, Lang, & Bucher, 2007). Anticipating and reacting to high attrition rates, 72 participants were enrolled.

Data cleaning and management was done to identify participants who responded to daily SMS surveys at least 189 times (70% of the 9-month trial). Fifteen (21%) of the 72 participants provided fewer than 100 responses. Another 14 participants (19%) provided between 100 and 188 responses. An additional four participants (9.7%) were removed because they did not respond at least 70% of the days during each 90-day time period. The final data set consisted of 39 participants: 18 in the No Intervention arm and 21 in the Intervention arm. Post-hoc analysis indicated the study was powered at 93%.

¹ NOTE: Faul, F., Erdfelder, E., Lang, A.-G., & Buchner, A. (2007). G*Power 3: A flexible statistical power analysis program for the social, behavioral, and biomedical sciences. *Behavior Research Methods*, 39, 175-191.

Data collection was done with Qualtrics™ (Provo, Utah) and analyses were done using Microsoft Excel (Redmond, Washington) and IBM SPSS Statistics for Macintosh (version 24, Chicago, Illinois).

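### The primary RM-ANOVA keeps only 39 of 72 participants, using a text-response cut-off absent from the protocol's analysis plan and applied largely after the day-90 grouping, with exclusions not shown by arm and no sensitivity analysis

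*SAP*

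**What the plan says.** The SAP's Data Analysis Plan applies two response rules before the primary RM-ANOVA.

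- Whole study: "Data cleaning and management was done to identify participants who responded to daily SMS surveys at least 189 times (70% of the 9-month trial". Fifteen participants with fewer than 100 responses and 14 with 100 to 188 fall below this.
- Each period: "An additional four participants (9.7%) were removed because they did not respond at least 70% of the days during each 90-day time period".

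The analysed set is 39 participants, 18 without intervention and 21 with it.

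The protocol treats these matters differently.

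- In Materials and Methods, 70% is a condition for compensation: "The participant will receive a pre-paid card if they respond to >70% of text messages over each 90-day cycle", together with attending the visit.
- In Data Analysis, the RM-ANOVA "will be conducted (assuming sufficient data is available", with a low rate of declined answers as the example. No per-person threshold is given.
- The one analysis exclusion named is a sexually transmitted infection diagnosed during the study. Such participants "will be removed from the study and their data will be excluded from analysis".
- Groups are formed on day 90 from the first 90 days of answers. The protocol then says: "Following the principle of intent-to-treat, data from those in the Bothersome Bleeding group will be assigned to the aygestin group", even when they do not take the drug.
- The fourth reply option each day is "Prefer not to answer today". The SAP does not say whether it counts as a response.

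**The concern.** Group membership is fixed by bleeding in days 1 to 90, but membership of the analysed set also depends on answering through days 91 to 270. In that time one group is offered three months of medication and then stops it, and the other is only observed. Continued answering could be related to bleeding, to tolerance of treatment or to keeping the implant. If so, the 39 are selected on something close to the outcome, possibly differently in the two groups.

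Appendix II provides for participants who have already had the implant removed, and the protocol's objective includes implant continuation. If texting stops at removal, which the documents do not state, anyone whose implant comes out before day 243 (180 + 63) fails the rule automatically.

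The SAP describes the rule in the past tense beside its resulting counts. The documents therefore do not show that it was set before the data were seen.

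**Working it through.** **Inputs.** From the SAP: 72 enrolled; 15, 14 and 4 removed; 39 analysed (18 + 21); cut-offs of 189 responses and 70% per 90-day period; power figures of 80% at N = 28 and 93% post hoc. From the protocol: grouping at day 90. Assumption: at most one answer per day.

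**The plan's own figures.**
- 15 + 14 + 4 = 33, and 72 − 33 = 39 = 18 + 21. Reproduces.
- 0.70 × 270 = 189. Reproduces.
- Power for the group-by-time interaction, with two groups, three measurements, f = 0.25, and correlation 0.5 and sphericity 1 assumed because the SAP states neither: λ = f² × N × 3 / (1 − 0.5).
  - N = 28: λ = 10.5, df 2 and 52, power 81.2%.
  - N = 39: λ = 14.625, df 2 and 74, power 92.9%, against the stated 93%. Both reproduce.
- 4/72 = 5.6%, not 9.7%. The figure 9.7% is 7/72, but removing seven would leave 36, so the count of four is the one consistent with 39.

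**Size of the restriction.** Removed: 33/72 = 45.8%. Kept: 39/72 = 54.2%.

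**What the rule amounts to.** 0.70 × 90 = 63 and 3 × 63 = 189, so meeting the per-period rule guarantees the overall one. The operative requirement is 63 of 90 in every period. Answers required after day 90: 2 × 63 = 126, and 126/189 = 66.7%. A participant with 90, 90 and 62 answers, the 62 falling in a later period, has 242/270 = 89.6% and is still removed.

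**Data set aside.**
- Answers from the 33, lower bound: 14 × 100 + 4 × 189 = 2,156, counting the 15 as zero.
- Upper bound: 15 × 99 + 14 × 188 + 4 × 242 = 5,085.
- Answers from the 39: 39 × 189 = 7,371 to 39 × 270 = 10,530.
- Share set aside: 2,156/(2,156 + 10,530) = 17.0% to 5,085/(5,085 + 7,371) = 40.8%.
- After day 90: each of the 14 has at least 100 − 90 = 10 answers and each of the four at least 189 − 90 = 99. Together that is at least 140 + 396 = 536 answers from 18 people.
- Two full periods hold at most 180 answers, so each of the four has at least 189 − 180 = 9 in every period. All three window means exist for them, and the RM-ANOVA could have included them.

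**Exclusions by arm.** If x of the 33 belonged to the no-intervention group, retention is 18/(18 + x) there and 21/(54 − x) in the intervention group. As x runs from 0 to 33, the first falls from 100% to 35% and the second rises from 39% to 100%. If some were never labelled, the split is less determined still. Strongly differential exclusion cannot be ruled out.

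**The case against.** The strongest reply is that the protocol expected heavy non-response. Its recruitment target is 30 active participants per arm, with up to 100 enrolled to reach 60, and 70% per 90-day cycle was already its compliance benchmark. The sufficiency wording could also be read per person. Of the 33 removed, 29 answered less than 70% overall and only four fell to the per-period rule alone, so the 242-answer case is an extreme. Some of the 33 may never have been classifiable at day 90, and the intent-to-treat sentence literally concerns people not taking the drug. The groups are not randomised, so no randomised balance is lost.

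Parts of this stand. The 70% figure was not invented for the SAP, although the payment condition is strictly more than 70%. The intent-to-treat sentence is supporting evidence only. The number removed after being labelled is unknown, anywhere from 0 to 33; the 18 are people with late answers, not people shown to have been labelled and then dropped. The 17% to 41% range pairs opposite extremes. The protocol gives declined answers their own count and no bleeding score, so what is open is whether they count towards 189.

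None of it supplies an analysis-set rule. The protocol does not define active or tie it to who is analysed, and a payment threshold is not an exclusion criterion. The lack of randomisation does not excuse a further selection step that can be avoided.

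**Conclusion.** The concern holds. The primary comparison rests on 54% of those enrolled, chosen by a rule that the protocol's analysis plan does not contain and that draws two-thirds of its required answers from after the grouping date. The resulting bias has unknown size and direction, and the documents do not allow it to be computed. The 93% power figure is reproducible for 39 participants under the assumed correlation and sphericity, but it says nothing about selection. The answer counts assume one answer per day. The 9.7% is a separate reporting slip and does not affect the 39.

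**What to change.** 1. Define the primary set as all participants who could be labelled at day 90, kept in that group whatever their later response count.
2. State the minimum of days 1 to 90 data needed for labelling, since Table I defines an episode as "One or more consecutive days during which bleeding or spotting was entered in the diary, bounded by bleeding-free days" and gaps affect it. The SAP's own 63 of 90, applied to that period only, is one option, with a lower minimum as a sensitivity analysis.
3. Fit a likelihood-based linear mixed model (group, window, group by window) to all available answers, weighting window means by days answered.
4. State that a declined answer is missing, not a bleeding value, and whether it counts as a response. State how answers after implant removal are handled.
5. Report the 39-person set as a sensitivity analysis.
6. Report exclusions, reasons and response counts by group and period, listing those never labelled separately, and compare the days 1 to 90 bleeding of those kept and removed. Say whether anyone was excluded for a sexually transmitted infection.
7. Correct 9.7% to 5.6%.

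The cost is SAP wording and one mixed model in SPSS, already in use, on existing data. The model relies on missing-at-random, which is doubtful if silence follows implant removal. Sparse responders add imprecise means, and the estimate may be less favourable. A 63-of-90 labelling minimum may itself exclude some of the 33. Confounding and regression to the mean from grouping on early bleeding would remain.
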